7.3 Adverse events: structurally assessed at each study visit

Some safety outcomes were structurally assessed at each study visit as part of the face-to-face interview and pelvic and bimanual examination. Laboratory test results will not be included because they are covered under the primary and secondary efficacy outcomes. The safety outcomes will be reported as the number of women who experienced the event at least once during the time period by study group. Differences between the randomisation groups will be assessed by Fisher's exact test. If the p-value is < 0.05, pairwise comparisons (also using Fisher's exact test) between study groups will be conducted. If an AE occurred more than once in individual women, the analysis will be repeated for the number of events (as opposed to number of women) per study group. All analyses will be done for three time periods: between the Enrolment and M2 visits (during product use), between the M2 and M6 visits (after cessation of product use), and for the overall follow-up period between the Enrolment and M6 visits.

Number of women	Group 1	Group 2	Group 3	Group 4	p-
Between Enrolment – M2	N=17	N=17	N=17	N=17	value ¹
Any patient-reported urogenital symptoms (n %)					
If yes, symptoms reported (n % for each) ² :					
– Burning when passing urine					
 Frequent urination or urgent need to urinate 					
– Blood in urine					
– Genital burning					
– Genital itching					
– Pain during sex					
– Lower abdominal pain					
– Unusual vaginal discharge					
– Sores in the genital and/or anal area					
(including buttocks)					
– Other (describe in footnote)					
Any abnormal findings during pelvic exam					
clinician-observed (n %)					
If yes, findings observed (n % for each) ² :					
– Abnormal (genital) odour					
 Enlarged/tender inguinal lymph node 					
 Condylomata (any location genitalia) 					
 Ulcers/blisters suggestive of STI on vulva 					
 Any other lesion on vulvar epithelium 					
 Abnormal vaginal discharge 					
–Vaginal mass (polyp, myoma, etc.)					
 Ulcers/blisters suggestive of STI in vagin 					
 Any other lesion on vaginal epithelium 					
 Abnormal cervical discharge/pus 					
 Any lesion on cervical epithelium 					
 Other (describe in footnote) 					
Any abnormal findings during bimanual exam					
clinician-observed (n %)					
If yes, findings observed (n % for each) ² :					
– Uterine mass					
– Adnexal mass					
- Uterine tenderness					
– Adnexal tenderness					
-Cervical motion tenderness					
-Other (describe in footnote)					
Diagnoses based on the above (but not including					
the efficacy endpoints) (n % for each):					
 Pelvic inflammatory disease (PID) 					
- Mucopurulent cervicitis					
- Genital ulcer disease (GUD)					
 Genital warts/condylomata 					

1. Fisher's exact test

2. Percentages can add to more than 100% because participants were allowed to give multiple answers or could have multiple conditions.

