6.4 Enrolment visit

The enrolment visit will be scheduled as soon as possible, and within a maximum of 3 days after completion of oral metronidazole treatment. This window of 3 days is needed in case the last day of oral metronidazole treatment is in the weekend or during menses. At the enrolment visit, the following procedures will take place:

- 1. Urine pregnancy and urinalysis dipstick testing. If pregnant, not eligible. If UTI, treat and do not yet randomise. Repeat wet mount (and collect Gram stain for Nugent scoring) and enrol based on new wet mount results as in 6.3.2.
- 2. Enrolment informed consent procedures;
- 3. Face-to-face interview (update on current medications, contraception and genital symptoms and baseline assessment of AEs and social harms)
- 4. Speculum examination with collection of vaginal swabs for vaginal pH measurement, wet mount, Gram stain Nugent scoring, TV culture and VMB assessments (see 8.2); endocervical swabs to store for potential NG/CT testing (if required for clinical reasons or for VMB interpretation); and a CVL to store for additional VMB assessments (see 8.2). If BV by Amsel

criteria, TV on wet mount or symptomatic vaginal candidiasis on wet mount, treat and do not yet randomise. Repeat wet mount (and collect Gram stain for Nugent scoring) and enrol based on new wet mount results as in 6.3.2.

- 5. Randomisation;
- 6. HIV/STI/BV risk reduction counselling plus explanation of the intervention that the participant was randomised to (including detailed explanations of potential side effects, and in the case of metronidazole, potential side effects when metronidazole is combined with alcohol use), provision of study products, and application of the first dose of the relevant intervention under supervision of a study staff member (and practice of vaginal self-sampling if in the frequent sampling group). Women will be asked to stay in the study clinic for a minimum of about 30 min after application of the first dose to identify and treat any immediate allergic reactions (these are exceedingly rare).
- 7. Reimbursement, and scheduling of the Day 7 visit;
- 8. Participant leaves the RU clinic;
- 9. Further laboratory testing:
 - Vaginal swabs and CVL: Initial processing and storage of a vaginal Gram stain for Nugent scoring at RU, and vaginal swabs and CVL for VMB and biofilm assessments at UoL (see 8.2);
 - Endocervical swabs: Initial processing and storage for potential local NG/CT testing;

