The tablet disintegrates inside the vagina, forming a gel which continually releases the prebiotics and probiotics, thus providing continuous nutrients and lactobacilli inside the vagina, favourable to their proper implantation and regeneration of the flora.

HOW DO I USE GYNOPHILUS® LP?

Wet the tablet in water to make insertion easier.

Insert a tablet deep in the vagina at night when going to bed.

GYNOPHILUS® LP INSTRUCTIONS FOR USE:

1 tablet every four days:

- · to regenerate the vaginal flora: 2 tablets treatment
- · to prevent relapse: 6 tablets treatment

Gynophilus® LP can be used:

- · after a local antifungal or antibiotic treatment
- at the same time as an oral treatment (generally antibiotic)

DURING TREATMENT:

- Discharge may occur a few hours after having inserted the tablet (it is advisable to wear a liner).
- Sexual intercourse possible 8 hours after insertion of the tablet.

PRACTICAL TIPS:

- Wash your hands carefully before and after administration of the product.
- Use soap with neutral or alkaline pH for your intimate hygiene routine.
- · Use your own bathroom linen (flannel, towel).
- · Preferably wear cotton underwear.
- Avoid vaginal douching.

DO NOT SWALLOW. KEEP OUT OF THE REACH OF CHILDREN.

PACK SIZE:

Aluminium blister pack containing 2 tablets.

COMPOSITION:

Each Gynophilus® LP tablets contains:

876,9 mg of Lcr Regenerans[®]

STORAGE:

Store below 25 °C.

Do not use after the expiry date on the pack

Manufacturer:

Probionov [name] - FRANCE

Distributor:

CE 0537

Distributor logo

01077XXP

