6.1 Intent-to-treat incidence rates of primary efficacy outcomes

All women at all study visits were tested for BV by Amsel criteria, BV by Nugent scoring, TV by wet mount, TV by InPouch culture and vaginal candidiasis by wet mount.

During follow-up, antibiotic and antifungal treatments were given as follows:

- BV was only treated when a woman had BV by Nugent score or modified Amsel criteria but also reported symptoms typical for BV (unusual vaginal discharge, fishy smell) or these were observed by the study physician during a pelvic examination. A diagnosis could almost always be made on the day of the study visit.
- TV was always treated when identified on wet mount or by TV culture. The wet mount results were always available on the day of the study visit, but the InPouch culture results only 5 days later. If a woman had tested negative by wet mount but positive by InPouch culture, she was asked to return to the RU clinic for treatment.
- Vaginal candidiasis was only treated when Candida was present on the wet mount and the participant reported symptoms that are typical for vaginal candidiasis (itching, curd-like discharge) or these were observed by the study physician during a pelvic examination. A diagnosis could almost always be made on the day of the study visit.

We will describe any antibiotic or antifungal use between randomisation and M2 and between M2 and M6 by indication, drug type and drug dosing schedule.

Each positive case during follow-up will be assessed separately to differentiate between incident infections and persistent infections. We will assess whether treatments were dispensed appropriately and whether participants adhered to the treatments.

The incidence of each primary outcome will be defined as follows:

- Incident BV by modified Amsel criteria: positive by modified Amsel criteria after having been negative by modified Amsel criteria at the previous visit or after a case of symptomatic BV (diagnosed by modified Amsel criteria or by Nugent score) was adequately treated.
- Incident BV by Nugent score 4-10: a Nugent score of 4-10 after a Nugent score of 0-3 at the previous visit or after a case of symptomatic BV (diagnosed by modified Amsel criteria or by Nugent score) was adequately treated.
- Incident BV by Nugent score 7-10: a Nugent score of 7-10 after a Nugent score of 0-6 at the previous visit or after a case of symptomatic BV (diagnosed by modified Amsel criteria or by Nugent score) was adequately treated.

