6.2 Intent-to-treat incidence rate ratios comparing product use groups to the control group

IRRs with 95% confidence intervals will be calculated comparing each product use group (groups 2-4) to the control group (group 1) using the IR function in STATA. In addition, IRRs with 95% confidence intervals will be calculated comparing each vaginal probiotic group (group 3 and 4) to the metronidazole group (group 2). As before, these IRRs will be calculated for each primary efficacy outcome and for each of the three time periods: between the Enrolment visit and the M2 visit (during product use), between the M2 visit and M6 visit (after cessation of product use) and for the entire study period after randomisation. They will be reported in the following table (one table for each time period):

	Group 2 vs 1 IRR (95% CI)	Group 3 vs 1 IRR (95% CI)	Group 4 vs 1 IRR (95% CI)	Group 3 vs 2 IRR (95% CI)	Group 4 vs 2 IRR (95% CI)
Incident BV by					
modified Amsel					
criteria					
Incident Nugent 4-10					
Incident Nugent 7-10					
Incident TV by culture					
Incident symptomatic					
vaginal candidiasis					

6.3 Per protocol incidence rate ratios comparing product use groups to the control group

A few significant protocol deviations occurred that could have an impact on the primary analysis results:

- CT/NG PCR testing was not available at the RU clinic and was outsourced to the National Reference Laboratory in Kigali, Rwanda. Test results were usually available only weeks after sample collection. We realised that this might be an issue early on and increased the sample size of each randomisation group to 17 instead of 15 to allow for exclusion of women who were randomised while having an ongoing CT or NG infection. Unfortunately, the number of women with a CT or NG infection in each randomisation group turned out to be higher than expected: 8/17 in Group 1, 7/17 in Group 2, 4/17 in Group 3, and 7/17 in Group 4 (Fisher's exact p = 0.53).
- Discrepancy between modified Amsel criteria and Nugent score at the Enrolment visit: Women could be enrolled if they had negative modified Amsel criteria after having completed the 7-day metronidazole treatment. Nugent scores became available later. In a handful of cases, women who were randomised because they no longer had BV by modified Amsel criteria turned out the have a Nugent score of 7-10 at the Enrolment visit.

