7.4 Adverse events: not structurally assessed

In addition to the safety outcomes that were structurally assessed, the study physician also asked the following questions at each study visit: Since your last study visit, did you experience any other new physical complaints or were you diagnosed with any other new conditions? Since your last study visit, have you taken any new medications? The answers given to those questions, and any other spontaneously reported adverse events, will be coded using MedDRA (version 19.0, March 2016) and will be reported in the same manner as described above for the structurally assessed adverse events.

8. Analyses of follow-up data: secondary efficacy outcomes

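### SAP 7.3 counts symptoms and exam findings without reference to Enrolment and mixes product irritation with infection symptoms; the all-cause table is valid as a net effect but needs supplementing

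*SAP*

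**What the plan says.** - **Counting rule (SAP 7.3).** "The safety outcomes will be reported as the number of women who experienced the event at least once during the time period", by study group, for Enrolment to M2, M2 to M6 and overall. Arms are compared by Fisher's exact test, with pairwise tests only if the four-group p-value is below 0.05. There is no new-onset or worsening condition.
- **Separation from efficacy (SAP 7.3).** "Laboratory test results will not be included because they are covered under the primary and secondary efficacy outcomes". The diagnosis rows are headed "Diagnoses based on the above (but not including" the efficacy endpoints. The symptom and examination rows carry no such exclusion.
- **Enrolment data (Protocol 6.4).** The interview updates genital symptoms and includes a "baseline assessment of AEs and social harms"; a speculum examination follows. SAP 4.2 tabulates symptoms at Screening, before metronidazole. SAP 4.3, collected at Enrolment, covers vaginal practices, menses and probiotics. Neither shows symptoms or findings at first dose.
- **Shared symptoms (SAP 6.1).** BV was treated only when a positive woman "also reported symptoms typical for BV (unusual vaginal discharge, fishy smell") or the physician observed these signs. Itching is listed as typical of candidiasis. Discharge, odour and itching are all rows in 7.3.
- **CT/NG (SAP 6.3).** Infections among randomised women were "8/17 in Group 1, 7/17 in Group 2, 4/17 in Group 3, and 7/17 in Group 4". SAP 6.3 and 6.4 deal with this for efficacy; 7.3 does not mention it.
- **Contrast (SAP 7.4).** The unstructured question is "did you experience any other new physical complaints"; 7.3 has no equivalent word for new.
- **Product effect (Protocol 15.3, Gynophilus leaflet).** "Discharge may occur a few hours after having inserted the tablet".

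**The concern.** A discharge, odour or itching row can fill in three ways: the product irritates, an infection recurs or is acquired, or the symptom was already there at first dose. SAP 7.3 does not tell these apart.

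The second route matters most, because the products are meant to reduce it. A product that prevents BV removes BV symptoms from its own arm while any irritation adds events to the same row, so the two pull in opposite directions. The first step of a separation is already in the SAP, which drops laboratory results and efficacy diagnoses but leaves their symptoms in.

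Safety against control is primary objective 1, and Protocol 3.2 says the pilot is meant to guide the choice of interventions for an efficacy trial. A reader needs to see whether a small difference in the safety rows means little irritation, or irritation offset by fewer infections.

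**Working it through.** The documents give no expected adverse event rate or power for safety, so there is no planned safety figure to reproduce. The one stated result nearby is the CT/NG comparison: 8 + 7 + 4 + 7 = 26, and 26/68 = 38.2%. The SAP gives Fisher p = 0.53; exact enumeration gives 0.544, a difference of no consequence.

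**Inputs**
- From Protocol 3.1: about 50% BV recurrence within 6 months; a 57% reduction with metronidazole vaginal gel, which disappeared after the gel was stopped.
- From SAP 6.3: 17 women per arm and the CT/NG counts.
- Assumed: recurrence r during product use, symptomatic share s of recurrences, background symptoms b, and product irritation i. Independence is also assumed.

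**Model for an any-symptom row.** P(event) = 1 − (1 − b)(1 − q)(1 − i), with q = rs in control and q = 0.43rs under a 57% reduction.

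**Step 1: partial masking.** Take b = 0 and i = 12%, a true excess of 12 points or about 2 women of 17. Control = rs; product = 1 − (1 − 0.43rs)(0.88).

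| r | s | Control | Product | Difference (points) |
|---|---|---|---|---|
| 50% | 0.3 | 15.0% | 17.7% | +2.7 |
| 50% | 0.5 | 25.0% | 21.5% | −3.5 |
| 50% | 0.7 | 35.0% | 25.2% | −9.8 |
| 20% | 0.3 | 6.0% | 14.3% | +8.3 |
| 20% | 0.5 | 10.0% | 15.8% | +5.8 |
| 20% | 0.7 | 14.0% | 17.3% | +3.3 |

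Products are used for 2 months, so the 50% is a 6-month figure applied to a shorter period. If the recurrence rate were constant, 50% at 6 months would give 1 − 0.5^(2/6) = 20.6% at 2 months, which is why 20% is shown. At 20% the difference shrinks at each s shown but does not reverse.

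**Step 2: irritation that cancels exactly.** i* = 1 − (1 − rs)/(1 − 0.43rs).
- r = 0.2, s = 0.25: 1 − 0.95/0.9785 = 3%.
- r = 0.5, s = 0.5: 1 − 0.75/0.8925 = 16%.
- r = 0.5, s = 1: 1 − 0.5/0.785 = 36%.

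**Step 3: dilution by background symptoms.** For a product with no BV effect, the difference is (1 − b)(1 − rs)i. With rs = 0.25 and i = 30% it is 22.5 points at b = 0, 18.0 at b = 0.20 and 14.0 at b = 0.38. Background symptoms shrink the difference but do not change its sign.

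**Step 4: CT/NG.** Prevalence is 47% in Group 1, 41% in Groups 2 and 4, and 24% in Group 3. If a quarter of infected women had symptoms, these would affect 11.8% of control and 5.9% of Group 3; if half, 23.5% and 11.8%. The documents do not give this share. The chance imbalance would make Group 3 look better; Groups 2 and 4 are close to control.

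**Step 5: power at 17 per arm.**
- p < 0.05 needs, for example, 5/17 v 0/17, 11/17 v 4/17 or 15/17 v 8/17.
- With i = 30%, r = s = 0.5 and b = 0, the planned row reads 25.0% v 37.5%; exact Fisher power is 6%.
- If product-caused events could be isolated cleanly over a 5% background, the row would read 5% v 33.5% (1 − 0.95 × 0.70). Power would be 44%, or about 41% by simulation once the four-group test must be passed first.
- With i = 15%, the planned row reads 25.0% v 24.1%. Clean isolation with no background gives 0% v 15%, and power of only about 10%.

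**The case against.** **All-cause counting is legitimate.** Protocol 12.1 defines an adverse event regardless of cause, and an all-cause count by randomised arm is a valid net comparison. This stands. A reader might infer that the table says nothing about product safety; the documents do not support that. What 7.3 lacks is anything beside the net count.

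**Eligibility limits carry-over.** Protocol 5.2 excludes women with genital ulcers, condylomata or other genital abnormalities at Screening or Enrolment. Protocol 6.4 withholds randomisation for BV by Amsel, TV on wet mount or symptomatic candidiasis. This largely stands, so pre-existing masses or lesions are a poor example. Residual symptoms, CT/NG-related symptoms and the few women with Nugent 7-10 at Enrolment (SAP 6.3) remain.

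**New onset may be implied.** Follow-up interviews ask for an update since the last visit, and the 7.4 question about other new complaints could imply that the structured items are new too. That is a possible reading, but 7.3 does not say it, and an ongoing symptom would still be reported.

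**Irritation can be seen elsewhere.** Genital burning, pain during sex and epithelial lesions have their own rows and are not among the BV symptoms in SAP 6.1. This stands in part; the discharge, odour, itching and 'any' rows are the ones affected. SAP 5 cross-tabulates several symptoms against infection at all visits, but not by arm.

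**The figures are borrowed.** The 57% comes from vaginal gel, whereas Group 2 took oral metronidazole (SAP 1.1), and the documents give no such figure for the probiotics. This stands: the working shows possible size, not expected size.

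**A tempting remedy fails.** Basing the main comparison on infection-negative visits would condition on something the products may change. On the illustrative 50% v 21.5% recurrence (0.43 × 50%), control would have fewer such visits in which to show an event. It would also drop itching at Candida-positive visits, although the SAP objective includes not increasing candidiasis.

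**Conclusion.** The point holds as a gap in what 7.3 displays. The table has no Enrolment reference, and its discharge, odour, itching and 'any' rows mix local irritation with symptoms of infection. The all-cause comparison is sound as a net effect but, standing alone, can dilute or partly mask irritation from a product that reduces BV.

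The mechanisms differ. Symptoms already present at Enrolment mainly dilute the contrast. So do CT/NG symptoms, apart from the chance imbalance favouring Group 3. Masking comes from infections that the product reduces.

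A reader might infer that an effective but irritating product would look as safe as control, or safer. That needs 6-month recurrence within a 2-month period, a product that matches the gel effect, and a sizeable symptomatic share. With 12% irritation and 20% recurrence, the excess falls to between 3.3 and 8.3 points for symptomatic shares of 0.3 to 0.7 and keeps its sign. The cancelling rate of 3% to 36% shows how far the result depends on assumptions.

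This is a worthwhile, low-cost improvement to a descriptive pilot. It makes the table easier to interpret; it does not make 17 per arm enough to establish safety. Nothing is claimed here about SAP 7.1 or 7.2.

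**What to change.** Amend SAP 7.3 as follows:

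1. Keep the all-cause rows by randomised arm, unchanged, as the main comparison.
2. Add a column with the Enrolment prevalence of each symptom and finding by arm, and state that the Enrolment visit itself is not counted as follow-up.
3. Add, for each row, the number of women whose event was absent at their Enrolment interview or examination, or had worsened since.
4. Add a supplementary, descriptive split of the symptom and finding rows by concurrent BV or TV status at the visit. Give Candida-positive events their own column and keep them as possible harm. A footnote should say that the split conditions on status after randomisation, which the products may alter, and is not a test of product safety.
5. Show the PID, cervicitis and cervical-discharge rows by CT/NG status at Screening.

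**Cost.** SAP wording and some programming. Symptoms and examination findings are collected at Enrolment, BV, TV and Candida are tested at every study visit, and CT/NG is tested at Screening. Judging 'worsened' needs a rule if severity was not recorded; otherwise use new onset only. The table becomes longer and the cells small, so items 2 to 5 should be read as description.

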Primary clinical endpoints will be the safety and preliminary efficacy of the study products, the latter defined as incidence of BV by Amsel criteria, BV by Nugent score (Nugent 7-10), intermediate microbiota (Nugent 4-6), TV by culture and symptomatic vaginal candidiasis (by wet mount) during follow-up. Secondary clinical endpoints will be membership of specific VMB clusters over time as determined by clustering analysis of all available Illumina MiSeq data, the presence over time of individual VMB bacteria (as determined by Illumina MiSeq), and the incidence of STIs (HIV, syphilis, HSV-2, CT, and NG), and UTI (by urinalysis dipstick) during the follow-up period. In addition, we will conduct focus group discussions (FGDs), in-depth interviews (IDIs) and a quantitative survey to address specific feasibility objectives (see 4.2 below).

Primary clinical objectives	Endpoints
1. To determine the safety of the three biomedical interventions compared to the control group.	 Self-reported solicited and unsolicited (serious) adverse events (AEs) and social harms Clinician-observed speculum exam findings
2. To determine the preliminary efficacy of the three biomedical interventions compared to the control group in reducing BV recurrence.	 BV by Amsel criteria, Nugent score 4-10, TV by culture and symptomatic vaginal candidiasis at any time during the intervention (Day 7, Month 1, Month 2) BV by Amsel criteria, Nugent score 4-10, TV by culture, and symptomatic vaginal candidiasis after cessation of the intervention (Month 6) Abnormal Nugent scores will be analysed as two categories (4-6 and 7-10) instead of one category (4-10) if statistical power permits.
Secondary clinical objectives	Endpoints
1. To determine which VMB changes at the molecular bacterial level are induced by initiation and cessation of the various interventions compared to the control intervention.	 Membership of specific VMB clusters (as determined by clustering analysis of all Illumina MiSeq data) over time The presence over time of individual VMB bacteria as determined by Illumina MiSeq (and, if funding permits, other molecular methods), including the PPMs streptococci, staphylococci, and E coli. The additional data points in the frequent self-sampling group will be analysed separately.
2. To determine preliminary	 Incidence of the following STIs between screening and

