12.3 Assessing AE/SAE severity and relationship to study products

The Principal Investigator is responsible for assessing the severity of AEs/SAEs occurring on study. The following criteria will be used:

- Mild: Transient or mild discomfort (<48 hours), no medical intervention/therapy required;
- Moderate: Mild to moderate limitation in activity, some assistance may be needed, no or minimal medical intervention/therapy required;

• Severe: Marked limitation in activity, some assistance usually required, medical Intervention or therapy required.

The Principal Investigator is responsible for determining the relationship of all AEs/SAEs with study product use based on the following criteria:

- Not Related: There is no temporal or causal relationship to the study product administration, and the AE/SAE is clearly explained by another cause (concurrent disease, concomitant medication, etc.);
- Probably Not Related (Unlikely): There is a temporal relationship to study product administration, but there is no reasonable causal relationship, and the AE/SAE is more likely explained by another cause (concurrent disease, concomitant medication, etc.);
- Possibly Related: The AE/SAE can be explained by another cause but the possibility of a relationship with the study product cannot be ruled out.
- Probably Related: There is a temporal and causal relationship between the study product and the AE/SAE, and the AE/SAE is more likely explained by the study product than by another cause;
- Definitely Related: There is a temporal and causal relationship between the study product and the AE/SAE, and the AE/SAE responds to withdrawal of the study product (and recurs with repeat administration of the study product).

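### Protocol 12.3 has adverse events graded for severity and relatedness, but SAP 7.3 and 7.4 summarise them by neither, so a severe non-serious event is not distinguished from a mild one

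*SAP*

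**What the plan says.** **What is collected.** Protocol 12.3 states: "The Principal Investigator is responsible for assessing the severity of AEs/SAEs occurring on study". The scale has three levels, mild, moderate and severe. The same section adds: "The Principal Investigator is responsible for determining the relationship of all AEs/SAEs with study product use based on the following criteria", with five categories from not related to definitely related.

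**What the endpoint is.** Safety is primary clinical objective 1 in the protocol's table of objectives and in SAP section 2. The endpoint is worded as "Self-reported solicited and unsolicited (serious) adverse events (AEs) and social harms", together with clinician-observed speculum findings. It names no severity or relatedness level.

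**What is analysed.** In SAP 7.3, patient-reported symptoms, pelvic and bimanual findings and the resulting diagnoses are "reported as the number of women who experienced the event at least once during the time period by study group". The four groups are compared by Fisher's exact test, with pairwise tests only if p < 0.05. If an event recurs in individual women, the analysis is repeated on the number of events. This is done for three periods: Enrolment to M2, M2 to M6, and Enrolment to M6. SAP 7.4 codes all other AEs in MedDRA, and these "will be reported in the same manner as described above for the structurally assessed adverse events". Neither section has a row, column or listing by severity or relatedness.

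The SAP contents list shows separate sections for serious adverse events (7.1) and social harms (7.2). Their text was not available for this review.

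**The concern.** The protocol asks for two judgements on AEs, and the sections that analyse non-serious AEs use neither. Serious and severe are different things here. Protocol 12.2 defines serious by outcome: death, threat to life, hospitalisation, congenital anomaly or disability. Protocol 12.3 defines severe by the effect on the woman: "Severe: Marked limitation in activity, some assistance usually required", with medical intervention or therapy required. A local vaginal reaction can be severe without being serious. Such an event falls under 7.3 or 7.4, where it is counted like a brief, mild instance of the same symptom.

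This matters for the trial's own purpose. Protocol 3.2 says the data are needed to choose interventions for a later efficacy trial. Participants have just been treated for bacterial vaginosis or *Trichomonas*, and the solicited list includes discharge, itching and burning, which can also come from recurrence or candidiasis. Ungraded counts may therefore be high in every group. Severity would then be the information that separates a well-tolerated product from a poorly tolerated one.

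**Working it through.** The plan states no figure on this point, and no sample size calculation was made (Protocol 4.3), so there is nothing to reproduce. The check is a comparison of the two texts, followed by an illustration.

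**Side by side**

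| Item | Protocol 12.3 | SAP 7.3 | SAP 7.4 |
|---|---|---|---|
| Severity | 3 grades | not used | not used |
| Relatedness | 5 categories, all AEs/SAEs | not used | not used |
| Unit counted | – | women with the event; events if recurrent | same as 7.3 |

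**Illustration.** The group size of 17 is from SAP 6.3. All event counts below are assumed and are not trial data.

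*Step 1, the planned table.* Suppose 8 of 17 women in every group report a given symptom. This is the most probable table given the margins, so the four-group Fisher test gives p = 1.00 and no pairwise test follows.

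*Step 2, the same women by grade.* Suppose all 8 are mild in three groups, while in the fourth k of the 8 are severe. A severe-only row would read 0, 0, 0, k.

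- Four-group Fisher: p = 4 × C(17,k) / C(68,k)
- Pairwise Fisher, 0/17 v k/17: p = 2 × C(17,k) / C(34,k)

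| k | Four-group p | Pairwise p |
|---|---|---|
| 3 | 4 × 680 / 50,116 = 0.054 | 2 × 680 / 5,984 = 0.23 |
| 4 | 4 × 2,380 / 814,385 = 0.012 | 2 × 2,380 / 46,376 = 0.10 |
| 5 | 4 × 6,188 / 10,424,128 = 0.002 | 2 × 6,188 / 278,256 = 0.044 |

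A marked imbalance in severe events can thus sit inside a row that shows no difference. Five against zero is also the smallest split against zero that reaches pairwise p < 0.05.

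*Step 3, what a zero would mean.* With no severe event among 17 women, the two-sided 95% Clopper-Pearson upper limit is 1 − 0.025^(1/17) = 19.5%. An empty row would give little reassurance about the true rate.

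**The case against.** Several things can fairly be said for the plan.

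- **The plan is not one crude count.** SAP 7.3 has separate rows for each symptom, each examination finding and diagnoses such as pelvic inflammatory disease, and it repeats the analysis on event counts when events recur. This stands. Severity is lost only within a row, but the repeat counts are ungraded too.
- **Serious events are handled elsewhere.** They have their own SAP section, and the Trial Steering Committee reviews each one (Protocol 13.2). A reader might infer that no planned safety table shows severity or relatedness. The documents do not support that, because the text of 7.1 and 7.2 could not be read. The gap shown is for severe but non-serious events in 7.3 and 7.4.
- **The SAP does not contradict the endpoint.** The endpoint names no grade, and Protocol 12.3 assigns grading without promising an analysis by grade. This also stands. The point is unused information, not an inconsistency.
- **The numbers are too small for tests by grade.** This is correct, as the table above shows, and the protocol calls the study descriptive. It argues for descriptive rows, not for leaving the grades out.
- **Not every 7.3 item may carry a grade.** No case report form is shown, and a scale built on activity limitation fits poorly with findings such as condylomata or a vaginal mass. The SAP should therefore say which items were graded.

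A reader might also infer a hole in the scale, with mild discomfort lasting 48 hours or more having no grade. The wording is "Mild: Transient or mild discomfort (<48 hours), no medical intervention/therapy required". The time limit can be read as explaining only the word transient, which leaves no hole. In any case the SAP already reports M6 attendance of 64 women (SAP 3.1). Rewording the scale at that stage could not change grades already given without re-grading by an unblinded investigator.

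**Conclusion.** The point holds for SAP 7.3 and 7.4. Severity and relatedness are required by the protocol but absent from the analysis of non-serious AEs, so the primary safety comparison cannot separate a severe event from a mild one of the same kind. It is a minor, inexpensive improvement and does not invalidate the planned comparisons.

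Its size cannot be taken from the documents, which give no AE counts. The illustration shows only that p = 1.00 in the planned row is compatible with 0, 0, 0 and 5 severe events. It would be wrong to infer that graded tests would reliably find such a difference, since 3 or 4 events against zero do not reach pairwise significance.

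The conclusion assumes that the grading in Protocol 12.3 was carried out and recorded. It makes no claim about 7.1 or 7.2.

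**What to change.** For each of the three periods, add descriptive rows by group to the 7.3 and 7.4 reporting, using the maximum severity per woman:

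1. women with at least one moderate or severe AE;
2. women with at least one severe AE;
3. for Groups 2 to 4 only, women with at least one AE judged at least possibly related. Group 1 has no study product, so the row has no meaning there.

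Add a note under the table that grading was by an unblinded investigator: Protocol 4.4 says clinicians cannot be blinded. State which 7.3 items were not individually graded. Do not base conclusions on formal tests by grade at 17 per group, and leave the wording of the mild grade as it is.

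The cost is three table rows per period and a footnote, using assessments the protocol already requires. Items found to have no individual grade need only be declared as such.
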